## **Period 2**

To evaluate the long-term safety, tolerability and efficacy of upadacitinib 15 mg QD in subjects with RA who have completed Period 1.

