### **Discontinuation of Study Drug and Continuation of Study Participation (Period 1 and Period 2)**

Subjects may discontinue study drug treatment, but may choose to continue to participate in the study (refer to Section 5.4.1 for additional details). Subjects who prematurely discontinue study drug should complete a Premature Discontinuation Visit (PD visit) as soon as possible, preferably within 2 weeks. Afterwards, subjects should follow the regular visit schedule as outlined in Table 2 and Table 4, and adhere to all study procedures except for dispensing study drug, PK sample collection, and blood sample collection for optional exploratory research and validation studies. In addition, all future rescue and efficacy-driven discontinuation criteria no longer apply; this includes 20% TJC/SJC calculations at Weeks 14 – 22, and Week 48 and thereafter, as well as CDAI calculation at Week 26, if applicable. If at any point a subject no longer wants to provide assessments (withdrawal of informed consent) following discontinuation of study drug, a second PD visit is not required.

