- Starting at Week 48, at least 20% improvement in BOTH TJC AND SJC compared to baseline is required to remain on study drug. Anyone who does not fulfill this criterion at 2 consecutive visits (starting at Week 48) must be discontinued from study drug.

In order to minimize missing data for efficacy and safety assessments, subjects who prematurely discontinue study drug treatment or study participation should complete a Premature Discontinuation visit (PD visit) as described in Section 5.1 (Overall Study Design and Plan: Description)

All attempts must be made to determine the date of the last study drug dose and the primary reason for discontinuation of study drug or study participation. The information will be recorded on the appropriate eCRF page. However, these procedures should not interfere with the initiation of any new treatments or therapeutic modalities that the Investigator feels are necessary to treat the subject's condition. Following discontinuation of study drug, the subject will be treated in accordance with the Investigator's best clinical judgment, irrespective of whether the subject decides to continue participation in the study.

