### **6.1.7 Toxicity Management**

The toxicity management of the AEs including AEs of special interest consists of safety monitoring (review of AEs on an ongoing basis, and periodical/ad hoc review of safety issues by a safety data monitoring committee), interruption of study drug dosing with appropriate clinical management if applicable, and discontinuation of the subjects from study drug. The management of specific AEs and laboratory parameters is described below.

For subjects who discontinued study drug but continued study participation and are instead on standard of care therapies, these toxicity management requirements do not apply (including alerts from the central lab) and any intolerability to standard of care therapies should be managed by the prescribing physician.

**Serious Infections:** Subjects should be closely monitored for the development of signs and symptoms of infection during and after treatment with study drug. Study drug should be interrupted if a subject develops a serious infection or an opportunistic infection. A subject who develops a new infection during treatment with study drug should undergo prompt diagnostic testing appropriate for an immunocompromised subject. As appropriate, antimicrobial therapy should be initiated, and the subject should be closely monitored. Re-challenge with study drug may occur once the infection has been successfully treated. If study drug has been interrupted for a serious infection for more than 14 consecutive days during the first 26 weeks, more than 21 days between Weeks 26 and 48 or more than 30 consecutive days thereafter, the subject must be discontinued from study drug. Subjects who develop active TB must be permanently discontinued from study drug.

**Gastrointestinal Perforation:** Subjects presenting with the onset of signs or symptoms of a serious gastrointestinal event should be evaluated promptly for early identification of

gastrointestinal perforation. If the diagnosis of gastrointestinal perforation is confirmed, the subject must be discontinued from study drug.

**Cardiovascular Events:** Subjects presenting with potential cardiovascular events should be carefully monitored. These events will be reviewed and adjudicated by an independent Cardiovascular Adjudication Committee in a blinded manner.

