9.1.2 Definitions of Missing Data Handling Approaches

Non-Responder Imputation (NRI) Approach

The NRI approach will categorize any subject who has missing value for categorical variables at a specific visit as non-responder for that visit. In addition, subjects who prematurely discontinue from study drug will be considered as non-responders for all subsequent visits after discontinuation.

Observed Cases (OC)

The OC analysis will not impute values for missing evaluations, and thus a subject who does not have an evaluation on a scheduled visit will be excluded from the OC analysis for that visit. In addition, OC will not include values after subject have switched study treatment or after premature discontinuation of study drug.

As Observed (AO)

The AO analysis will not impute values for missing evaluations, and thus a subject who does not have an evaluation on a scheduled visit will be excluded from the AO analysis for that visit. Regardless of treatment switching or premature discontinuation of study drug, all observed data will be used in the analysis.

Mixed Effect Model Repeat Measurement (MMRM)

The repeated measure analysis will be conducted using mixed model including observed measurements at all visits. The mixed model includes the categorical fixed effects of

treatment, visit and treatment-by-visit interaction, main stratification factors at randomization, and the continuous fixed covariates of baseline measurement. An unstructured variance covariance matrix will be used. The parameter estimations are based on the assumption of data being missing at random and using the method of restrictive maximum likelihood (REML). [REDACTED]

[REDACTED]

Multiple Imputations (MI)

The MI analysis will impute missing data multiple times under appropriate random variation and thus generate multiple imputed "pseudo-complete" datasets. Results will be aggregated across the multiple imputed datasets, overcoming drawbacks of the single imputation methods. [REDACTED]

[REDACTED]

Linear Extrapolation for Radiographic Data

For radiographic data (i.e., mTSS-based endpoints), linear extrapolation will be applied to subjects who were rescued or prematurely discontinued study drug, where the x-ray at the time point of interest after rescue or PD will be imputed assuming a linear relationship between baseline, the x-ray collected at rescue or PD, and the time point of interest.

To summarize the use of different missing data handling approaches in the analysis:

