9.4 Long-Term Efficacy Analysis

Assessments to evaluate long-term efficacy will be analyzed for the following measures at each visit until completion of the study

- ACR20/50/70 response rates;
- Change from baseline in individual ACR components;
- Change from baseline in DAS28 (CRP);
- Change from baseline in DAS28 (ESR);
- Change from baseline in CDAI and SDAI;
- Change from baseline in morning stiffness (severity and duration);

- Proportion of subjects achieving LDA and the proportion of subjects achieving CR based on DAS28 (CRP), DAS28 (ESR), SDAI, and CDAI criteria;
- Proportion of subjects with change from baseline in HAQ-DI ≤ -0.3 and ≤ -0.22 , respectively;
- Proportion of subjects with no concomitant corticosteroid use (among subjects with corticosteroid use at baseline);
- ACR/EULAR Boolean remission.

Additionally, assessment for the evaluation of radiographic changes in Period 2 will occur at Week 96 and every 96 weeks thereafter (or Premature Discontinuation visit):

- Change from baseline in modified Total Sharp Score (mTSS);
- Proportion of subjects with no radiographic progression (defined as change from baseline in mTSS of ≤ 0);
- Change from baseline in Radiographic joint space narrowing and joint erosion scores.

Descriptive statistics will be provided for each treatment group sequence as defined in Section 9.1.1. These include the number of observations, mean, standard deviation, 95% CI, median, minimum, Q1, Q3 and maximum for continuous endpoints; and frequencies and percentages with 95% CI using normal approximation for binary endpoints. Plots by treatment group sequence over time up to Week 48 will be provided.

No missing data imputation will be applied. All efficacy analyses will be based on As Observed (AO) analysis.

For Week 26 reporting, long-term efficacy analysis will only be presented up to Week 48.

Table 7 below provides the overview of the long-term efficacy analyses to be performed on different endpoints.

Table 7. Summary of Efficacy Variables and Corresponding Analyses for Long-Term Efficacy Analysis

Efficacy Variables	Analysis Method
Binary Endpoints:	

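### After Week 48 efficacy is summarised only As Observed, so response on study drug cannot be separated from response after study drug was stopped

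*SAP*

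**What the plan says.** Protocol 4.0 gives the Period 2 aim: "To evaluate the long-term safety, tolerability and efficacy of upadacitinib 15 mg QD". Protocol 5.6.1 adds that the extension should allow maintenance of response to both study drugs to be assessed.

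SAP 9.4 then rules for the long-term set: "No missing data imputation will be applied. All efficacy analyses will be based on As Observed (AO) analysis". SAP 9.1.1 and Table 7 agree. SAP 9.1.2 defines AO so that "Regardless of treatment switching or premature discontinuation of study drug, all observed data will be used in the analysis". On grouping, SAP 9.4 says: "Descriptive statistics will be provided for each treatment group sequence as defined in Section 9.1.1". The five sequences in SAP 9.1.1 are named by study drug, alone or with a switch. None is for time off study drug.

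Visits off study drug are expected. Protocol 5.1 says: "Subjects may discontinue study drug treatment, but may choose to continue to participate in the study". Those who do so follow the regular visit schedule, in Period 2 as well (Table 4 note). Protocol 5.4.1 adds a compulsory stop for insufficient joint-count improvement: "Anyone who does not fulfill this criterion at 2 consecutive visits (starting at Week 48) must be discontinued from study drug". The same section leaves later treatment to the investigator, and Protocol 6.1.7 refers to subjects who "discontinued study drug but continued study participation and are instead on standard of care therapies".

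**The concern.** Period 2 is meant to show whether response is maintained on the study drugs. A percentage that mixes visits on and off drug in unreported proportions does not show that. From Week 48 the protocol itself moves non-responders off drug, and their later visits on other therapy still count under the sequence they left.

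Other parts of the plan treat the same problem differently:

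- A protocol switch between study drugs has its own sequence. Stopping study drug for outside therapy has none.
- Long-term safety (SAP 10.1.3 and 10.2) is attributed to the treatment received at the time of the event, and treatment-emergent events end 30 or 70 days after the last dose. Long-term efficacy has no such limit.
- To Week 48, SAP 9.3.1 uses non-responder imputation (NRI) for binary endpoints, with AO as description. After Week 48 only AO remains.
- SAP 7.0 tabulates discontinuations in Period 2 but not how many subjects are off drug at each efficacy visit. SAP 6.3 counts concomitant medication only to 14 days after the last dose, so therapy started later does not appear there.

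**Working it through.** The plan states no figure for this point, so there is nothing to reproduce. The textual chain is complete: AO is the only method (SAP 9.1.1, 9.4, Table 7); AO includes visits after drug discontinuation (SAP 9.1.2); subjects off drug may keep attending (Protocol 5.1); SAP 7.0 counts Period 2 participants whether or not they stopped study drug in Period 1; and no sequence holds off-drug time.

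The possible size can only be illustrated. All inputs are assumptions:

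- r_on, response among those on study drug: 40% or 60%
- d, share of the sequence off study drug at a visit: 10%, 20% or 30%
- f, share of those off drug who still attend: 50% or 100%
- r_off, response among off-drug attenders: 20%, 40% or 60%

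Everyone on drug is taken as observed. The three rates are:

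- AO = [(1 − d) × r_on + d × f × r_off] / [(1 − d) + d × f]
- On-drug rate = r_on
- NRI after drug discontinuation = (1 − d) × r_on

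One case in full, with r_on 60%, d 20%, f 100% and r_off 20%: AO = 0.80 × 0.60 + 0.20 × 0.20 = 0.52; on-drug rate = 0.60; NRI = 0.80 × 0.60 = 0.48.

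| r_on | d | f | r_off | AO | On-drug | NRI | AO − NRI | AO − on-drug |
|---|---|---|---|---|---|---|---|---|
| 40% | 10% | 100% | 20% | 38% | 40% | 36% | +2 | −2 |
| 60% | 20% | 100% | 20% | 52% | 60% | 48% | +4 | −8 |
| 60% | 20% | 100% | 60% | 60% | 60% | 48% | +12 | 0 |
| 60% | 30% | 50% | 20% | 52.9% | 60% | 42% | +10.9 | −7.1 |
| 60% | 30% | 100% | 20% | 48% | 60% | 42% | +6 | −12 |
| 40% | 30% | 100% | 60% | 46% | 40% | 28% | +18 | +6 |

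The table contains the extremes of all 36 combinations (2 × 3 × 2 × 3): AO − NRI runs from 2 to 18 points and AO − on-drug from −12 to +6.

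The signs follow from the formulas. AO is never below NRI: its numerator is at least (1 − d) × r_on and its denominator at most 1. AO minus the on-drug rate equals w × (r_off − r_on), where w = d × f / [(1 − d) + d × f] is the off-drug share of observed visits. Its sign therefore depends only on whether off-drug attenders do better or worse than those on drug.

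**The case against.** The case for leaving the plan alone has several parts.

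- **AO is legitimate and openly defined.** A summary regardless of treatment is a reasonable choice for an extension, and SAP 9.1.1 rules out testing in this set. This stands. The gap is that AO is the only summary and carries study-drug labels.
- **The on-drug rate has its own bias.** Dropping visits after discontinuation removes the subjects whom the Week 48 rule takes off drug for non-response, so that rate is enriched for responders. This stands, and it argues against replacing AO with an on-drug main analysis.
- **The defined Observed Cases (OC) method does not fit.** SAP 9.1.2 says "OC will not include values after subject have switched study treatment or after premature discontinuation of study drug". Used as written, OC would empty the three switch sequences after the switch. This stands; the on-drug summary needs its own wording.
- **There is partial coverage.** SAP 9.3 handles Period 1 with NRI for binary endpoints and linear extrapolation for radiographic ones. SAP 7.0 gives Period 2 drug discontinuation separately from study discontinuation, with reasons. This stands to Week 48; discontinuation totals do not show who is off drug at a given efficacy visit.

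A reader might infer that subjects who respond to another biologic will be shown as upadacitinib responders. The documents do not establish that. Protocol 5.2.3.2 prohibits all biologics in both periods. The sentences on commercial adalimumab in Protocol 5.1 sit under withdrawal of consent and follow-up, and only waive a safety call. Against that, Protocol 5.4.1 leaves treatment after stopping to the investigator, 6.1.7 expects standard of care, and 5.6.1 calls adalimumab standard of care. Use of a biologic by a continuing participant is thus possible but unresolved. The point does not need it, because any other therapy raises the same problem.

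**Conclusion.** The point holds as a gap in reporting. After Week 48 the planned efficacy tables mix response on and off study drug, and nothing planned lets a reader separate the two. The gap from an NRI rate is about 2 to 18 points and from the on-drug rate about −12 to +6 points. Both ranges rest wholly on assumed stop, attendance and response rates.

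Two stronger readings are tempting. The first is that AO inflates long-term efficacy. It does so only relative to counting stoppers as non-responders; relative to the on-drug rate the direction is open. The second is that the distortion must grow each year. That would require off-drug attenders to accumulate, whereas subjects off drug may leave and so drop out of the AO denominator.

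The primary endpoints, the ranked key secondary endpoints and type I error are untouched. The additions are worth making because Period 2 efficacy has no other analysis, but the trial's main conclusions do not depend on them.

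**What to change.** Keep AO. In SAP 9.4 and Table 7 add:

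1. For binary endpoints, an analysis that counts subjects as non-responders after premature discontinuation of study drug, with protocol switches kept within the sequence.
2. An on-drug companion summary that excludes visits after premature discontinuation but keeps visits after a protocol switch, defined separately from OC. State beside it that it is enriched for responders because of the Week 48 rule.
3. The number of subjects off study drug at each visit, by sequence.

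The data are already to be collected: Protocol 5.2.3 requires medications received during the study to be recorded, and 5.4.1 calls for the date of the last dose. The cost is SAP wording, extra tables, and smaller denominators in the on-drug summary at late visits.

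Separately, Protocol 5.2.3.2 (Biologic Therapies) should be reconciled with 5.1 (withdrawal and follow-up), 5.4.1 and 6.1.7, so that it is clear whether the prohibition applies to participants who have stopped study drug. Which rule should apply is for the sponsor to settle.

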9.5 Efficacy Variables Definitions and Conventions

9.5.1 ACR Criteria

ACR criteria are a commonly used standard criteria set mentioned in the guidance of American College of Rheumatology to evaluate the effectiveness of investigation drug in RA clinical trials. It is a composite measurement calculated based on the improvement over a set of core measurements.

ACR20 is defined as at least 20% improvement (compared to baseline values) in tender and swollen joint counts and at least 20% improvement in 3 of the remaining 5 core set measures (subject global assessment of pain, subject global assessment of disease activity, physician global assessment of disease activity, subject assessment of physical function and acute phase reactant hsCRP).

ACR50 and ACR70 are similarly defined with at least 50% and 70% improvement, respectively.

A subject will be classified as an ACR20 (ACR50, ACR70) responder, if the following conditions are met:

1. $\geq 20\%$ (50%, 70%) improvement from baseline in tender joint count (TJC68) and
2. $\geq 20\%$ (50%, 70%) improvement from baseline in swollen joint count (SJC66) and
3. $\geq 20\%$ (50%, 70%) improvement from baseline in at least 3 of the following 5:
 - patient's assessment of pain
 - patient's global assessment of disease activity (PGA)
 - physician's global assessment of disease activity (PhGA)
 - patient's self-assessment of physical function (i.e., measured by Health Assessment Questionnaire (HAQ-DI score))
 - Acute-phase reactant value CRP

There are seven components to be evaluated to define an ACR response. Missing values for each component can occur due to a missed visit or due to dropout from the study. Depending on the pattern of the missing components, ACR responses may be or may not be determined using observed values only.

9.5.2 Joint Evaluation

Anatomical joints are evaluated for swelling and tenderness at every study visit. The 34 anatomical joints in [Table 8](#) are assessed in this study for both the left and right side of the body.

Table 8. Anatomical Joints Assessed for Calculation of Tender and Swollen Joint Counts (TJC68 and SJC66)

Temporomandibular	Sternoclavicular	Acromio-clavicular	Shoulder
Elbow	Wrist	Metacarpophalangeal I	Metacarpophalangeal II
Metacarpophalangeal III	Metacarpophalangeal IV	Metacarpophalangeal V	Thumb Interphalangeal
Proximal Interphalangeal II	Proximal Interphalangeal III	Proximal Interphalangeal IV	Proximal Interphalangeal V
Distal Interphalangeal II	Distal Interphalangeal III	Distal Interphalangeal IV	Distal Interphalangeal V
Hip ^a	Knee	Ankle	Tarsus
Metatarsophalangeal I	Metatarsophalangeal II	Metatarsophalangeal III	Metatarsophalangeal IV
Metatarsophalangeal V	Great Toe/Hallux	Interphalangeal II	Interphalangeal III
Interphalangeal IV	Interphalangeal V		

a. Hip joints are not assessed for swelling.

At each study visit, a joint evaluator assessed whether a particular joint was "tender or painful" where presence of tenderness was scored as "1" and the absence of tenderness was scored as "0," provided the joint was not replaced ("9") or could not be assessed ("NA") due to other reasons (e.g., post-corticosteroid joint injection). The total tender joint count (TJC68), which is based on 68 joints, will be derived as the sum of all "1s" and proportional extrapolation will be used to impute joint counts for the joints that are replaced or not assessed. A similar method will be followed for the derivation of total swollen joint count (SJC66), which is based on 66 joints as the hip joints are excluded. Thus, the range for TJC68 will be 0 to 68 and 0 to 66 for SJC66.

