Starting at Week 26 (after Week 26 assessments have been performed) and thereafter, two intra-articular, intramuscular, intravenous, trigger point or tender point, intra-bursa, and intra-tendon sheath injections of corticosteroids, dosage and frequency per standard of care, are allowed. However, joint injections should be avoided within 21 days prior to the next scheduled study visit to avoid confounding effects of systemic absorption of intra-articular corticosteroids. For the analysis of the TJC and SJC, injected joints will be considered "not assessable" for 3 months from the time of the intra-articular injection.

Starting at Week 26 (after Week 26 assessments have been performed) and thereafter, initiation of or change in corticosteroids, NSAIDs, acetaminophen/paracetamol is allowed as per local label. For RA flare treatment, no more than 3 consecutive days of systemic corticosteroids (maximum dose of 0.5 mg/kg/day of prednisone or its equivalent) is allowed, after which subject should resume their usual daily oral corticosteroid dose.

Starting at Week 48 (after Week 48 assessments have been performed) and thereafter initiation of or change in csDMARDs is allowed as per local label (restricted to oral or parenteral MTX, sulfasalazine, hydroxychloroquine, chloroquine and leflunomide, and restricted to concomitant use of up to 2 csDMARDs except the combination of MTX and leflunomide; see Inclusion Criterion 9, Section 5.2.1).

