### **Corticosteroids**

Oral corticosteroids > 10 mg prednisone/day or equivalent are NOT allowed up to Week 26. Intra-articular, intramuscular, intravenous, trigger point or tender point, intra-bursa, and intra-tendon sheath corticosteroids are NOT allowed up to Week 26.

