### *SJC Assessment*

An assessment of 66 joints ([Appendix E](#)) will be done by directed physical examination at visits specified in [Table 2](#) and [Table 4](#). The joints to be examined for swelling are the same as those examined for tenderness, except the hip joints are excluded. Joint swelling will be classified as present ("1"), absent ("0"), replaced ("9") or no assessment ("NA").

Any injected joints will be considered as "not assessed" ("NA") for 3 months from the time of the intra-articular injection.

If possible, the TJC and SJC should be performed by an independent and blinded joint assessor who should not perform any other study related procedures.

In order to minimize variability, the same independent joint assessor should evaluate the subject at each visit for the duration of the trial as much as possible. A back-up independent joint assessor should be identified. The independent joint assessors should be a qualified medical professional (e.g., nurse, physician's assistant, physician). Any other joint assessor must be trained and competent in performing such assessments. It is the responsibility of the Investigator to ensure that all assessors are qualified and trained to perform joint assessments. If the independent assessor is not available, the pre-identified back-up assessor should perform such assessments.

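### SAP 9.5.2 prorates steroid-injected joints from the uninjected ones, which lowers TJC68 and SJC66 after Week 26 whenever the injected joint was active

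*SAP*

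**What the plan says.** **When injections are allowed.** Under Corticosteroids, Protocol 5.2.3.2 states that "intra-tendon sheath corticosteroids are NOT allowed up to Week 26". Protocol 5.2.3.1 then opens this route: "Starting at Week 26 (after Week 26 assessments have been performed) and thereafter, two intra-articular, intramuscular, intravenous, trigger point or tender point" and similar injections are permitted. From the same visit, systemic corticosteroids may be started or changed.

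**Status of an injected joint.** Protocol 5.3.1.1, SJC Assessment: "Any injected joints will be considered as 'not assessed' ('NA') for 3 months from the time of the intra-articular injection". Protocol 5.2.3.1 says the same for the analysis of both counts.

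**How it is scored.** SAP 9.5.2 sets aside a joint that "could not be assessed ('NA') due to other reasons (e.g., post-corticosteroid joint injection"), and for the total count "proportional extrapolation will be used to impute joint counts for the joints that are replaced or not assessed". SJC66 is derived the same way.

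**What the missing-data rules cover.** In SAP 9.1.2, NRI makes a missing value a non-response, and "subjects who prematurely discontinue from study drug will be considered as non-responders for all subsequent visits after discontinuation". For Period 1, SAP 9.3.1 adds only treatment switching at rescue. Continuous data after a switch become LOCF. Binary data become non-response after a Week 14, 18 or 22 switch, and the last pre-rescue response after a Week 26 switch. No rule mentions a steroid injection or a change in steroid use.

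**Where the counts are used.** Every ACR response needs the required improvement in both TJC68 and SJC66 (SAP 9.5.1). SAP 9.3.1 compares upadacitinib with adalimumab, by randomised group, at visits from Week 26 to Week 48.

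**The concern.** Proration assumes that an unassessed joint is as likely to be active as the assessed ones. That is reasonable for a replaced joint. A joint injected for active disease has been selected because it was tender or swollen, so its absence carries information that proration discards. The count falls although nothing has been observed in that joint, and the fall is credited to the assigned drug.

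At stake are the ACR rates and joint-count changes at Weeks 30 to 48, and the As Observed summaries. The protocol's summary of changes says csDMARD changes were restricted so that the comparison with the active comparator stays unbiased to the end of Period 1. The steroid route from Week 26 has no matching rule in the analysis. Nor will the planned tables show the problem: SAP 6.3 tabulates concomitant medication by generic name, and SAP 9.4 reports only steroid-free proportions among baseline users. Neither isolates injections, or starts or increases after Week 26.

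**Working it through.** No figure in the plan rests on this rule, so there is none to reproduce.

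**1. The rule as a formula.** Let N = 68 (TJC) or 66 (SJC), t = active joints, and k = injected joints that were active. The prorated count is (t − k) × N/(N − k). As a check, if none of the N − k assessed joints is active the result is 0, and if all are active it is N. These are the ranges that SAP 9.5.2 states.

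**2. The fall.** t − (t − k) × N/(N − k) = k(N − t)/(N − k). This is positive for every t below N and at most k, that is, at most one joint per injected active joint. All t from k to N − 1 were checked for k = 1 and 2. Injecting an inactive joint moves the count slightly upward (5 becomes 5 × 68/67 = 5.07).

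**3. Who can carry the effect in the primary Period 1 analysis.**
- Not 20% better on both counts at Week 14, 18 or 22: switched, then a non-responder (binary) or LOCF (continuous).
- CDAI above 10 at Week 26, either active arm: switched, and later data overwritten.
- CDAI ≤ 10 at Week 26: stays on randomised drug, and the subject's own later counts are used.

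Among subjects still on randomised drug, only the last group contributes new counts. They have few active joints, so one or two joints are a large fraction. As Observed analyses (SAP 9.1.2, 9.4) have no such filter.

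**4. Worked example in that group.** Baseline is 10 tender and 10 swollen, now 4 and 4: 60% improvement, ACR70 joint criteria not met. Four and four sum to 8 even if all lie within the 28 joints, which fits CDAI ≤ 10 if the two global scores add at most 2. Inject two joints that are both tender and swollen:
- TJC68 = (4 − 2) × 68/66 = 2.06, a 79% improvement.
- SJC66 = (4 − 2) × 66/64 = 2.06, a 79% improvement.

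Both ACR70 joint criteria are now met. With one injection TJC68 is 3 × 68/67 = 3.04, and the improvement (69.6%) just misses. From a baseline of 11 and 11, one injection is enough: 4 is a 63.6% improvement, while 3.04/11 and, for SJC66, 3 × 66/65 = 3.05 over 11 both give 72.3%.

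**5. How often a threshold can be crossed.** For each TJC68 baseline from 6 to 68 (63 values), the table counts those with at least one current count that crosses the tender-joint threshold only through proration:

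| Criterion | k = 1 | k = 2 |
|---|---|---|
| ACR20 | 30 | 53 |
| ACR50 | 31 | 63 |
| ACR70 | 50 | 63 |

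Per baseline, at most one such count exists for k = 1 and two for k = 2.

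**6. Arm-level size, on assumed inputs.** The documents give no injection rates. The product is (still on drug in LDA) × (injected) × (threshold crossed):
- low: 0.30 × 0.05 × 0.10 = 0.15 points
- central: 0.40 × 0.10 × 0.20 = 0.8 points
- high: 0.50 × 0.20 × 0.30 = 3 points

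This is inflation within one arm, not a difference between arms.

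**The case against.** **Controlled claims are untouched.** This stands. Injections are barred up to Week 26, every ranked endpoint is at Week 12 or Week 26, continuous Period 1 comparisons carry nominal p-values only, and Week 26 reporting shows this analysis set only to Week 26.

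**The striking case cannot arise as stated.** A reader might take a subject at the entry minimum, 6 tender and 6 swollen with no change, inject two joints, and find 4 × 68/66 = 4.12 and 4 × 66/64 = 4.13: a 31% improvement that satisfies both ACR20 joint criteria. The documents do not support that example. Such a subject fails the Week 14 joint test, is switched, and is a non-responder afterwards. Reaching those counts on randomised drug would need a response by Week 26 and then a full relapse.

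**Proration is close to scoring a treated joint as quiet.** True: in the example the count would be 2 rather than 2.06. But the protocol declares the joint uninterpretable for 3 months. Proration assigns it 2/66 = 0.03 of a joint, which in effect assumes that the injection worked completely and credits the study drug.

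**The effect is bounded.** Two joints must be unassessed at the same time to give the two-joint effect, so it lasts about 13 of the 22 weeks from Week 26 to Week 48. The allowance of two also covers routes that need not make a joint unassessable, and the text does not say whether it is a total or per route. Both points limit the size and leave the mechanism intact.

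**The remedy has its own bias.** Also fair: carrying forward an active status assumes no benefit from the injection, and counting steroid use as non-response is a choice of estimand. That is why the second element is proposed as a sensitivity analysis.

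**Conclusion.** The concern holds as a defect in one derivation rule. Whenever an active joint is injected, SAP 9.5.2 lowers the count by up to one joint per injected joint, and no rule in SAP 9.1.2 or 9.3.1 handles the injection or new or raised steroid use. The shift enters joint-count change as improvement. It alters an ACR response only near a threshold, and only if 3 of the 5 other components are also met, so meeting the joint criteria is not in itself a response.

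The effect is confined to exploratory visits after Week 26. On the assumed inputs above it inflates an arm's response rate by about 0.15 to 3 percentage points.

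A reader might infer that injections go to the weaker arm and pull the two arms together. The documents do not support this: they give no injection rates, sites and subjects stay blinded through Period 1, and subjects doing poorly up to Week 26 have already been switched. The direction between arms cannot be determined.

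One limit remains: SAP 9.5.2 names proration only for TJC68 and SJC66, so the handling of an unassessed joint in the 28-joint indices is not stated and is not quantified here.

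**What to change.** - **SAP 9.5.2:** keep proportional extrapolation for replaced joints and joints unassessed for other reasons. For an injected joint, carry forward its last pre-injection tender and swollen status through the 3-month period. The example above then stays at 4 and 4 (60%).
- **SAP 9.3.1:** add one sensitivity analysis for Weeks 30 to 48 in which a subject is a non-responder from the date of a steroid injection, or of a start or increase of systemic corticosteroids, after Week 26.
- **Reporting:** tabulate that steroid use by randomised arm, so that a reader can judge size and direction.

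Dates, route and dose are already recorded under Protocol 5.2.3, so the cost is SAP wording and a little programming, with no new data and no change to conduct. The downside is slightly lower response rates after Week 26, and carry-forward may overstate activity in a joint that truly improved.
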